## **1. Current Status of Clinical Trials and Research Objectives**

### **1.1 Research Status**

#### **1.1.1 Significance of Visual Perceptual Learning Training for Diabetic Retinopathy Patients**

Diabetic retinopathy (DR) is one of the most common chronic complications of diabetes and a leading cause of visual impairment in adults. In China, the prevalence of DR among diabetic patients is as high as 23%, with 3 ~ 4 million patients losing their vision annually due to DR, severely impairing their visual function and quality. Traditional research has focused on diabetic retinal vascular lesions, with vascular endothelial changes being the only clinically successful therapeutic target for DR patients. Current clinical treatments primarily address retinal vascular damage. However, we have observed that even after surgical treatment or retinal laser photocoagulation, DR patients with stable conditions still experience significant visual dysfunction, lacking further treatment options to improve visual function. This highlights the urgent need to explore effective rehabilitation methods for visual dysfunction in DR patients after clinical treatment stabilization.

#### **1.1.2 Domestic and International Progress in Visual Perceptual Learning**

Visual perceptual learning (VPL) training refers to a method of improving the visual system's ability to perceive external visual information through repeated specific visual tasks. In 2014, Sabel BA and Gudlin J conducted a randomized clinical trial on "vision restoration training" for glaucoma patients, demonstrating significant improvement in visual function in the training group compared to the control group. Sabel BA proposed the "residual vision activation theory," suggesting that in cases of retinal or visual cortex damage (e.g., glaucoma, stroke, amblyopia, age-related macular degeneration), repeated stimulation can enhance electrical conduction and synchronization among partially damaged neural synapses and downstream neural networks, leading to partial recovery of visual function. The visual system can actively adapt to and reflect changes in the external environment. When synaptic strength and quantity change and persist over time, this process is termed neuroplasticity. Its manifestations include induced dendritic growth or shortening, changes

in dendritic density, functional adjustments, and subsequent cortical reorganization and neurovascular regeneration. Studies have also shown that amblyopic patients can improve visual function through occlusion therapy or training, and even adult amblyopia may benefit from repeated perceptual learning. Yan and Zhou J conducted a randomized clinical trial on 23 myopic subjects, training the non-dominant eye at the cutoff frequency. Post-training, subjects showed improved contrast sensitivity and visual acuity at the trained spatial frequency, with effects lasting at least four months. These results suggest that VPL may offer a non-invasive training method to compensate for optical defects in mild to moderate myopia. Aimola L demonstrated that perceptual learning could partially improve visual perception in stroke patients, mitigating visual field defects caused by stroke. Age-related visual decline is common, and VPL can effectively improve near reading ability in individuals with early presbyopia symptoms. These studies indicate that the visual system retains plasticity across age groups, and VPL is the most widely used method to modify visual system plasticity and promote visual function recovery.

### **1.1.3 Mechanisms of Perceptual Learning Training**

Visual perception learning training refers to the method of improving the visual system's ability to perceive external visual information by continuously performing specific visual training tasks. The neural mechanism of visual perception learning has always been a research focus and difficulty in this field, although a lot of exploration has been conducted from the aspects of neurophysiology and neurobiology, it is still very unclear. There are mainly four theories: (1) the plasticity theory of the primary cortex: perceptual learning can make the neural encoding of stimuli in the primary cortex more accurate; (2) Reweighting Theory: By readjusting the weights of stimulus information in visual processing, the theory aims to enhance the efficiency of utilizing such information. (3) Reverse Hierarchy Theory: Visual signals are expressed in a top-down manner by feedback from the higher cortex to the primary cortex; (4) Dual plasticity theory: Perceptual learning may trigger the plasticity of the visual cortex towards stimulus attributes and task types. However, in fact, more research has not integrated different models into a unified perspective, and several issues highly

related to the core mechanism of VPL have become increasingly controversial. Scholars have trained macaques on direction recognition tasks . Compared with untrained macaques, the neurons in the V4 region of the trained macaques showed stronger responses and improved direction recognition ability after training. There are also studies using functional magnetic resonance imaging (fMRI) to investigate brain area activation during contrast discrimination task training . In the early stages of training, there is strong activation in the higher visual cortex, while in the later stages, activity in the lower visual cortex increases, indicating that visual perception learning training can activate corresponding brain areas to improve visual function. However, the relationship between the lower and higher visual cortices is complex and requires further research to prove.

The current clinical treatment methods are often difficult to make the visual function of patients with diabetes retinopathy (DR) fully recover to the normal level, and lack of follow-up treatment methods to further improve the visual function. How to find an effective way to restore the visual function of DR patients after damage is an urgent problem to be solved. This study conducted online remote visual perception learning training based on Internet cloud computing for DR patients who were in stable condition after surgery, and comprehensively evaluated the changes of visual perception function of DR patients before and after training by using perceptual function detection combined with OCT and psychological scale. The purpose was to evaluate the improvement effect of visual perception training on DR patients' visual function and influencing factors, and provide guidance strategies for the evaluation, follow-up and rehabilitation treatment of visual function after DR clinical treatment.

## **1.2 Research Objectives**

- 1.2.1** To explore the improvement of visual perceptual function in DR patients through VPL training.
- 1.2.2** To provide guidance for visual function recovery in DR patients with visual impairment.

## **2. Type of Study Design**

Prospective, randomized controlled clinical study.

### **3. Inclusion and Exclusion Criteria for Subjects**

#### **3.1 Inclusion Criteria:**

- (1) Pre-treatment diagnosis of moderate-to-severe non-proliferative or proliferative DR, with the affected eye having undergone pan-retinal photocoagulation at least 4 weeks prior or vitreoretinal surgery at least 8 weeks prior, with stable conditions and no macular edema or recurrent retinal hemorrhage.
- (2) Best-corrected ETDRS visual acuity (BCVA)  $\geq 0.1$ .
- (3) Clear refractive media.
- (4) Age  $\leq 65$  years, able to understand and cooperate with examinations and training.

#### **3.2 Exclusion Criteria:**

- (1) Significant refractive media opacity or other ocular diseases affecting visual function (e.g., high myopia, glaucoma, strabismus, amblyopia, macular degeneration).
- (2) History of psychiatric disorders affecting cognitive function, alcoholism, or traumatic brain injury.
- (3) Postoperative ocular complications within 8 weeks prior to testing.

#### **3.3 Elimination Criteria:**

- (1) Temporary refusal of examination or withdrawal from the study.
- (2) Incomplete examination records.

### **4. Expected Number of Cases Required**

Sample Size: 24 cases (estimated using G\*Power analysis, increased to 36 to account for potential dropout rates).

### **5. Experimental Methods**

#### **5.1 Grouping**

Subjects are randomly assigned to the Visual Perceptual Learning Training (VPLT) group or the Control Group (CG) using random number generation.

#### **5.2 Study Design**

Only the surgical eye is included (for bilateral surgery, the eye with better vision meeting inclusion

criteria is selected). The VPLT group undergoes 40 minutes of daily monocular VPL training for 3 months, with follow-ups at 1 and 3 months. The CG receives no training and is followed up after 3 months.

### **5.3 Assessments:**

Non-contact intraocular pressure measurement.

Ultra-widefield laser scanning fundus examination to exclude glaucoma and new hemorrhages.

Refractive correction for BCVA.

Optical coherence tomography (OCT) and OCT angiography (OCTA) for retinal blood flow and structural parameters.

Visual perceptual function assessment using a Matlab R2016a-based program, including:

Grating acuity (GA) at 0.8 contrast.

First-order motion stimulus perception sensitivity (1stM) at 2.0 c/d spatial frequency.

Second-order contrast stimulus perception sensitivity (2ndS) at 1.0 c/d spatial frequency.

Second-order motion stimulus perception sensitivity (2ndM) at 2.0 c/d spatial frequency.

Hospital Anxiety and Depression Scale (HADs) and Low Vision Quality of Life Questionnaire (LVQOL), administered by the same researcher.

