## **10. Adverse Event Recording, Reporting, and Follow-up**

Any serious adverse events are reported immediately to the clinical trial leader, with detailed documentation of timing, handling measures, and outcomes.

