## **11. Statistical Analysis Plan**

Statistical analysis was performed based on the per-protocol (PP) principle. Data are presented as mean  $\pm$  SD for normally distributed continuous variables, median ( $P_{25}$ ,  $P_{75}$ ) for non-normally continuous variables, and frequency (percentage) for categorical variables. The Shapiro-Wilk test was employed to assess the normality of the continuous variables. For normally distributed variables, between-group differences were assessed using unpaired t-test. Repeated measures analysis of variance (ANOVA) and simple effects analysis were conducted to examine changes in visual perceptual function and psychological status before and after VPL training. For each participant, the magnitude of improvement for each visual perceptual function ( $\Delta$ GA,  $\Delta$ 1stM,  $\Delta$ 2ndS,  $\Delta$ 2ndM) was calculated using the formula:  $\Delta I = 20 \log_{10} (Post-training Measure / Pre-training Measure)$  dB. Spearman correlation analysis was performed to evaluate the relationships among general demographic characteristics, visual perceptual function, retinal structure and blood flow parameters,

and psychological scale scores. Multivariable linear regression models were then constructed with  $\Delta$ GA,  $\Delta$ 1stM,  $\Delta$ 2ndS, and  $\Delta$ 2ndM as dependent variables to identify factors associated with training efficacy.

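### Non-serious eye events need not be recorded or tabulated by arm, so the plan as written cannot support a statement on the safety of the training

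*Combined protocol and SAP*

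**What the plan says.** **Adverse events.** The title of Section 10 covers recording, reporting and follow-up of adverse events in general. Its whole content is one sentence: "Any serious adverse events are reported immediately to the clinical trial leader, with detailed documentation of timing, handling measures, and outcomes". Events that are not serious are not mentioned. Section 7 adds a study-level stop for safety risks, with no threshold and no source of data.

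**Eye examinations.** Section 5.3 is one undivided list: eye pressure (IOP), fundus examination, refraction for BCVA, OCT and OCTA, perceptual tests and questionnaires. The fundus entry reads "Ultra-widefield laser scanning fundus examination to exclude glaucoma and new hemorrhages". No item carries a visit label. Section 5.2 follows the training arm at 1 and 3 months and the control arm at 3 months only. Section 6 takes the listed indicators as the clinical observation, yet says follow-up is by telephone.

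**Entry and removal.** Section 3.1 requires eyes "with stable conditions and no macular edema or recurrent retinal hemorrhage", and Section 3.2 excludes glaucoma. Section 3.3 gives two grounds for elimination: "Temporary refusal of examination or withdrawal from the study" and "Incomplete examination records".

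**Analysis.** Section 11 opens with "Statistical analysis was performed based on the per-protocol (PP) principle". The repeated measures ANOVA is "conducted to examine changes in visual perceptual function and psychological status before and after VPL training". Retinal structure and blood flow are named only in the correlation analysis. There is no safety set and no safety table.

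**The concern.** The trial enrols eyes recently treated for diabetic retinopathy and gives one arm 40 minutes of training a day for 3 months, about 60 hours per patient (40 min x 90 days / 60, taking 3 months as 90 days). A hemorrhage, edema or pressure rise found at an outpatient visit need not meet any definition of serious, and eye strain or headache from training would not. Under Section 10 nobody is asked to write these down.

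Two things are at stake. First, the trial could report a benefit and have nothing to say about harm, although it lists examinations that could show some of it. An event that was never collected cannot be recovered at the analysis stage. Second, such events could also lower the perceptual measures. Without a record of them, disease change cannot be separated from the effect of training, and patients lost after an event cannot be told apart from patients lost for other reasons.

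**Working it through.** The plan gives no safety figure to reproduce. The check is mainly a comparison of sections, followed by a calculation of what a recorded result could support.

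**1. Follow each kind of non-serious event through the plan.**

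| Event | Examination that could show it (5.3) | Visit stated in 5.3? | Record required (10)? | Safety summary by arm (11)? |
|---|---|---|---|---|
| New hemorrhage | Fundus examination | No | No | No |
| Macular edema | OCT | No | No | No |
| Pressure rise | Non-contact IOP | No | No | No |
| Loss of acuity | BCVA | No | No | No |
| Eye strain, headache | None | n/a | No | No |

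The end of the background in Section 1.1 describes evaluation before and after training with OCT, which suggests a repeat OCT. Nothing places the fundus or IOP check at 3 months, and a telephone contact (Section 6) cannot perform any of these examinations.

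**2. How a patient with an event can leave the analysis.** Section 3.3 eliminates those who withdraw, refuse examination or have incomplete records. Section 11 then analyses per protocol, with no intention-to-treat or safety set beside it. The event itself is not a ground for elimination; withdrawal or missing data after it is.

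The room for such losses can be read from Section 4, which raises 24 cases to 36. The 24 cannot be reproduced, because effect size, alpha, power and test are not given. The step to 36 corresponds to a loss of 1 - 24/36 = 33.3%, that is 12 of 36 patients. Read as a simple mark-up it is 24 x 1.5, or 50%.

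**3. Equal chance of being noticed.** Training arm: two follow-ups (1 and 3 months). Control arm: one (3 months). Asking about events at every contact would give the training arm two opportunities to report and the controls one, so a table by arm would not compare like with like.

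**4. What recording would buy.** Input: 18 trained patients, assuming 36 / 2; the allocation ratio is not stated. With no event among n patients, the one-sided 95% upper bound is 1 - 0.05^(1/n).

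- n = 18: 1 - 0.05^(1/18) = 15.3%
- n = 12 (24 / 2, if only the 24 remain): 1 - 0.05^(1/12) = 22.1%

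The chance of seeing at least one event is 1 - (1 - p)^n. The documents give no rate, so p is an assumed range:

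| True rate p | n = 18 | n = 12 |
|---|---|---|
| 5% | 60% | 46% |
| 10% | 85% | 72% |
| 20% | 98% | 93% |

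The trial is too small to establish safety, but large enough to be likely to show an event that affects one trained patient in ten. Both calculations require every patient counted in n to have been asked and examined.

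**The case against.** The strongest reply is that the plan does look for harm. IOP, BCVA, OCT and the fundus are all listed, Section 6 makes them the clinical observation, and Section 7 stops the study if safety risks arise. Section 10 is silent on non-serious events; it does not forbid recording them. Section 11 also has a general sentence assigning unpaired t-tests to differences between groups for normally distributed variables, which could be read to include IOP or BCVA. All of this is fair, and it means that harm might be seen. It does not supply a visit, a record or a table, and an unspecified t-test on a continuous measure would not count hemorrhages or complaints.

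A reader might infer more: that the fundus check removes eyes that bleed during the trial. The documents do not support that. *Exclude* beside glaucoma is ordinary wording for ruling a condition out and matches the entry rules in Sections 3.1 and 3.2, while Section 3.3, where removal is set out, does not name hemorrhage. The word is ambiguous because no visit is attached and Section 6 carries the same list into follow-up, but ambiguity is all that can be claimed. Nor do the documents name glaucoma as a condition that ends stability; it is an exclusion criterion only.

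A reader might also want a size for the resulting bias in the perceptual comparison. No defensible figure exists. The documents give no event rate, no loss per event and no standard deviation, and equal losses of similar eyes from both arms would leave the difference between arms roughly unchanged.

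**Conclusion.** The point holds as a gap in safety recording and reporting. Three things together make it: the only recording provision covers serious events, the eye examinations have no visits or recording rule for findings after randomisation, and the analysis section has no safety summary. The documented way for affected patients to disappear is withdrawal or incomplete records combined with the per-protocol rule, not the fundus check.

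No figure stated in the plan changes. What changes is the conclusion that the trial can draw: from no statement on non-serious harm to a modest one, an upper bound of about 15% if none of 18 trained patients has an event. That bound rests on equal allocation and complete ascertainment. The change should be made because it is cheap and the missing data cannot be rebuilt later; it does not by itself call the efficacy result into question.

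**What to change.** (a) **Section 5.3.** State the visits at which the fundus, IOP, BCVA and OCT checks are done. State that exclusion for glaucoma or new hemorrhage is an eligibility check, and that a later finding does not remove a randomised patient from the analysis. This concerns the analysis only and is not a rule on continuing training.

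(b) **Section 10.** Record all adverse events, serious or not, with the same question at the same time points in both arms: at minimum the common 3-month contact. Report any 1-month data from the training arm separately unless controls are asked then too. From the listed examinations, record new hemorrhage, macular edema, IOP and change in BCVA at 3 months. Reconcile Section 5.3 with the telephone follow-up in Section 6, since these findings need an examination.

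(c) **Section 11.** Tabulate these by arm for all randomised patients, showing how many were not assessed. Show the perceptual comparison with and without eyes that had such an event.

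The cost is wording, a few form fields, slightly more data entry and one extra table. If a 3-month examination visit is not already intended, (b) also needs that visit. Section 14 planned completion for August 2024. If follow-up is over, the eye findings may still be drawn from existing examination records and the table in (c) remains possible, but complaints that were never asked about are lost, and the report should say so.

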## **6. Clinical Observation, Follow-up, and Measures to Ensure Subject Compliance**

**Clinical Observation:** Indicators as described in the experimental methods.

**Follow-up:** Conducted via telephone.

**Compliance Measures:** Detailed contact information is collected during hospitalization, with timely follow-up via phone or WeChat post-surgery.

## **7. Criteria for Discontinuing Clinical Research and Regulations for Ending Clinical Research**

**Discontinuation Criteria:** Subjects may withdraw at any time. The study must be terminated immediately if safety risks arise.

**Ending Criteria:** The study concludes when the last subject completes the final follow-up.

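### Section 3.3 eliminates patients for a temporary refusal or incomplete records, and no section provides for 3-month outcomes after a training stop, so obtainable outcomes can drop out of a per-protocol-only analysis

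*Combined protocol and SAP*

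**What the plan says.** Four parts of the combined protocol and SAP bear on this.

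- **Section 3.3 (elimination).** The first ground is "Temporary refusal of examination or withdrawal from the study". The second is "Incomplete examination records". Elimination is not defined, and nothing limits these grounds to the time before randomisation.
- **Section 7 (discontinuation).** For the individual patient it says "Subjects may withdraw at any time". It does not mention stopping training while staying in follow-up.
- **Section 5.2 (design).** "The VPLT group undergoes 40 minutes of daily monocular VPL training for 3 months, with follow-ups at 1 and 3 months". The control group has no training and a single follow-up at 3 months.
- **Section 11 (analysis).** "Statistical analysis was performed based on the per-protocol (PP) principle". No second analysis set and no method for missing outcomes is given.

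Section 6 plans contact by telephone and WeChat, with no rule for patients who stop training or decline an examination. Section 4 takes 24 cases, "increased to 36 to account for potential dropout rates", and states no rate.

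**The concern.** A refusal that the plan itself calls temporary can be put right by rebooking. Section 3.3 gives it the same consequence as leaving the study. The incomplete-records ground can then remove a patient who has a valid 3-month result but lacks something else. Because Section 11 has only a per-protocol analysis, no other analysis brings these patients back.

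The second gap is an omission. A VPLT patient who tires of the daily sessions but would still attend at month 3 has no defined status. Staff are not told to examine that patient.

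The two arms are not equally exposed. Only VPLT patients can stop training, and only they have a 1-month visit, so on a literal reading of 3.3 only they can be eliminated over a 1-month examination. If those lost are the patients who gain least, the VPLT patients who remain look better than the arm as randomised. An outcome that was not measured cannot be recovered by a later choice of analysis set, so collection has to be settled as well as analysis.

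**Working it through.** **1. The plan's own figure.** The 24 cannot be reproduced, because Section 4 gives no effect size, SD, alpha, power, test or allocation ratio. The step from 24 to 36 can be read in two ways:
- N/(1 − d): 24/(1 − d) = 36 gives d = 1 − 24/36 = 33.3%.
- N(1 + d): 24(1 + d) = 36 gives d = 36/24 − 1 = 50%.

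On the first reading the plan allows for losing 12 of 36. The documents do not say which reading was meant.

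**2. Burden by arm.** Section 5.2 gives 40 minutes daily for 3 months. Taking 3 months as 91 days, 40 × 91 / 60 = 60.7 hours per VPLT patient, against none in the control group. VPLT has two follow-ups and the control group has one.

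**3. Possible shift in the VPLT mean.** Assumptions: 18 per arm (Section 5.1 states no ratio), 4 VPLT patients unmeasured, their mean change d SD below the full-arm mean M, and no selective loss among controls. Let m be the mean of the 14 who are measured:
- [14m + 4(M − d)] / 18 = M, so m = M + 4d/14.
- d = 0.5: 4 × 0.5 / 14 = 0.14 SD.
- d = 1: 4 × 1 / 14 = 0.29 SD.

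**4. A second model as a check.** Assume no true effect, a fraction q of the VPLT arm lost, and a correlation r between completion and outcome under a normal selection model. The shift is r × φ(z_q) / (1 − q), where z_q is the normal quantile at q. For q = 1/3 it is 0.11 SD at r = 0.2 and 0.27 SD at r = 0.5, a range close to that in step 3.

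**5. Precision.** For an unpaired t-test at two-sided alpha 0.05 and an assumed true difference of 1.0 SD, power is 0.83 with 18 v 18, 0.65 with 12 v 12, and 0.53 with 18 v 6. The last case puts all 12 losses in the VPLT arm and is an extreme.

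**The case against.** A reader might infer that the plan treats a patient who stops training as lost, collects nothing afterwards, and so never obtains the outcome, mainly in the VPLT arm. The documents do not support that reading:

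- No section says that a training stop is a withdrawal. The sentence in Section 7 is an ordinary right-to-withdraw statement, and Section 5.2 does not make the 3-month follow-up depend on continued training.
- No section says that collection ends after elimination. The term is undefined. Since incomplete records can be judged only once examinations were due, it may mean removal from the analysis and no more.
- No figure in the documents shows unequal loss. Untrained controls may also fail to return.
- The contact planned in Section 6 is not limited to patients who are still training.
- The 33% loss, the 18 per arm, the count of 4 and the deficit are readings or assumptions, not statements of the plan.

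All of this stands, and it limits the point on training stops to an omission. It does not answer Section 3.3. There the plan states a rule: a temporary refusal eliminates. If elimination means removal from the analysis only, a patient whose outcome was obtained, or could be by rebooking, is still dropped under Section 11.

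**Conclusion.** The point holds in two parts of different strength. First, on explicit text, Section 3.3 makes a temporary refusal and incomplete records grounds for elimination, and with the per-protocol-only analysis this discards patients whose 3-month outcome could be had. Second, by omission, the plan neither separates stopping training from leaving the study nor provides for the 3-month assessment after a training stop. The unequal opportunity for loss follows from the design; unequal loss itself is plausible but unquantified.

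The illustrative size is 0.14 to 0.29 SD in favour of VPLT. It rests wholly on the assumptions in the working and shows what could happen, not what will. In a trial of 36 that is enough to justify a change of wording, which the sponsor should make.

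**What to change.** - **Section 3.3(1):** delete the temporary-refusal ground. Rebook a declined examination within a stated month-3 window that is the same in both arms.
- **Section 3.3(2):** do not eliminate a patient for incomplete records; use the outcomes that are available.
- **Section 7:** state that stopping training does not end follow-up, and that only withdrawal of consent to further data collection does. Invite every other randomised patient to the 3-month assessment, and record the reason and date of stopping by arm. Because Section 6 describes follow-up by telephone while Section 5.3 includes imaging, say that this assessment is attended in person.
- **Section 11:** include these outcomes in an analysis by randomised group. Without this change and the one to 3.3(2), the newly collected outcomes could still be discarded.

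The cost is protocol wording and some rebooking through the telephone and WeChat contact already planned; no new assessment is needed. The estimated effect may be somewhat smaller once patients who stopped training are measured and counted.
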